#### 8.6.4. Risk assessment

Figure 9, Figure 10 and Figure 11 give the probability of not meeting each holding rule 1 and 2 for the subjects in 1 vaccine group.

# Figure 9 Evaluations based on 6 subjects per group – Risk assessment curve for 1 formulation based on the proposed safety holding rules (dose-escalation safety lead-in steps)

The Figure 9 illustrates that, with 6 subjects per study group:

• Each holding rule 1a-c and 2a-c has more than 82% chance of being met for vaccination with a true incidence rate above 25% and has more than 53% chance of not being met for vaccination with a true incidence rate below 10%.

# Figure 10 Evaluations based on 30 subjects per group – Risk assessment curve for 1 formulation based on the proposed safety holding rules (staggered step)

The Figure 10 illustrates that, with 30 subjects per study group:

- Each holding rule 1a-c has more than 78% chance of being met for vaccination with a true incidence rate above 5% and has more than 74% chance of not being met for vaccination with a true incidence rate below 1%.
- Each holding rule 2a-c has more than 80% chance of being met for vaccination with a true incidence rate above 25% and more than 93% chance of not being met for vaccination with a true incidence rate below 10%.

Safety holding rule after 200, 250, 300, 350 subjects

The Figure 11 illustrates that, with 200-350 subjects per study group:

The holding rule 1a has a chance ranging from 3% (with 350 subjects) to 13% (with 200 subjects) of not being met for vaccination with a true incidence rate below 1% and has more than 98% chance of being met for vaccination with a true incidence rate above 2%.

#### 8.6.5. Safety review team (SRT)

The SRT is a GSK's Central Committee responsible for on-going safety monitoring of the entire project and will meet on a regular basis throughout the duration of the study. In order to keep blinded all people involved in the conduct, cleaning and final analysis of the study, the SRT will monitor safety in a blinded manner. The GSK Biologicals' SRT and iSRC chair will jointly review blinded safety data. If no potential holding rules (e.g. 1a, 1b or 1c, Table 26) or safety concerns are identified during this blinded review, then review of unblinded data by iSRC team may not be required and study can proceed with the next step. Should there be any concerns that would require the evaluation of unblinded safety data, the iSRC will perform unblinded review of safety data and proceed as specified in the iSRC charter.

Refer to the iSRC Charter for details about the safety assessment committees evaluation.

#### 8.6.6. Internal Safety Review Committee (iSRC)

As this will be the first time that the *S. aureus* candidate vaccine will be administered in humans, the study will enroll and vaccinate subjects in several steps (see also Figure 7 and Figure 8). An iSRC authorised by the GSK's VSMB will review unblinded data and holding rules have been established to ensure the safety of the subjects in the study. Conditional review of unblinded data by iSRC (i.e. in case of any safety concern, see also Section 8.6.5) can be performed after any step of the study, as applicable. Predefined unblinded review by iSRC will be performed on Day 8 after vaccination Visit 1 of the fourth group of dose-escalation safety lead-in and on Day 8 after vaccination Visit 1 of the last subject of the approximately first 40 subjects of staggered enrolment of the PoP.

Details on safety assessment committees process is further described in the iSRC Charter.

# 9. DISCONTINUATION CRITERIA

# 9.1. Discontinuation from the study

From an analysis perspective, a 'withdrawal' from the study refers to any subject who did not come back for the concluding visit/was not available for the concluding contact foreseen in the protocol.

All data and samples collected until the date of withdrawal/last contact of the subject will be used for the analysis.

A subject is considered a 'withdrawal' from the study when no study procedure has occurred, no follow-up has been performed and no further information has been collected for this subject from the date of withdrawal/last contact.

Investigators will make attempts (3 telephone calls [e.g. once every 3 days] and a certified letter to the last known address or local equivalent methods) to contact those subjects who do not return for scheduled visits or follow-up.

Primary reason for study withdrawal will be documented in the eCRF. The investigator will document whether the decision to withdraw a subject from the study was made by the subject himself/herself, or by the investigator, as well as which of the following possible reasons was responsible for withdrawal:

- Adverse events requiring expedited reporting (refer to Section 12.5.9.2 for details)
- Unsolicited non-serious adverse event
- Solicited adverse event
- Protocol deviation
- Withdrawal by subject, not due to an adverse event\*
- Migrated/Moved from the study area
- Lost to follow-up

- Sponsor study termination
- Other (specify)

\*In case a subject is withdrawn from the study because he/she has withdrawn consent, the investigator will document the reason for withdrawal of consent, if specified by the subject, in the eCRF.

Subjects who are withdrawn from the study because of SAEs/AEs must be clearly distinguished from subjects who are withdrawn for other reasons. Investigators will follow subjects who are withdrawn from the study as result of a SAE/AE until resolution of the event (see Section 12.5.11).

## 9.2. Discontinuation of study vaccine(s)

A 'withdrawal' from the study vaccine(s) refers to any subject who does not receive the complete treatment, i.e. when no further planned dose is administered from the date of withdrawal. A subject withdrawn from the study vaccine(s) may continue further study procedures (e.g. safety, efficacy or immunogenicity) if planned in the study protocol, as deemed appropriate by the investigator.

Primary reason relative to premature discontinuation of the study vaccine(s) will be documented on the Vaccine Administration page/screen of the eCRF. The investigator will document whether the decision to discontinue further vaccination was made by the subject himself/herself, or by the investigator, as well as which of the following possible reasons was responsible for withdrawal:

- Adverse event requiring expedited reporting
- Non-serious adverse event (specify)
- Unsolicited non-serious adverse event
- Solicited adverse event
- Not willing to be vaccinated
- Other (specify).

## 9.3. Lost to follow-up

A subject will be considered lost to follow-up if he or she repeatedly fails to return for scheduled visits and is unable to be contacted by the study site.

The following actions must be taken if a subject fails to return to the clinic for a required study visit:

• The site must attempt to contact the subject and reschedule the missed visit as soon as possible and counsel the subject on the importance of maintaining the assigned visit schedule and ascertain whether or not the subject wishes to and/or should continue in the study.

- Before a subject is deemed lost to follow-up, the investigator or designee must make every effort to regain contact with the subject (where possible, 3 telephone calls and, if necessary, a certified letter to the subject's last known mailing address or local equivalent methods). These contact attempts should be documented in the subject's medical record.
- Should the subject continue to be unreachable, he/she will be considered to have withdrawn from the study with a primary reason of lost to follow-up and last day of actual contact be recorded on termination page.

# 10. STATISTICAL CONSIDERATIONS

## 10.1. Sample size determination

#### 10.1.1. Hypotheses related to primary and secondary objectives

For the primary safety objective no statistical hypotheses are applicable.

Two statistical hypotheses will be tested for the secondary efficacy objective.

- 1. Null Hypothesis : Hazard Ratio (HR) ≥1 after the second vaccination Alternative Hypothesis: HR <1
- 2. Null Hypothesis : Hazard Ratio (HR) ≥1 after the first vaccination Alternative Hypothesis: HR <1

If the first hypothesis is statistically significant, also the second hypothesis will be tested in a sequential procedure. In case the first hypothesis is not significant no conclusions will be taken with respect to the second hypothesis. Both hypotheses will be tested using the log rank test.

For the first hypothesis referring to the key efficacy endpoint two sequential analyses will be done following a Group Sequential Design using the O'Brien-Fleming spending function (with 48% and 100% of the total planned events). *(Amended 6 October 2022)* 

At the interim analysis the first hypothesis will be tested spending 1.61% alpha and 8.83% beta (this means a power equal to about 91%). At the final analysis the alpha will be 5.89% and the beta 11.17% (this means a power equal to about 89%). Overall after two sequential analyses the cumulative alpha will be 7.5% and the cumulative beta 20% (or power equal to 80%).

The assumptions to test the first hypothesis on the HR after the second vaccination are:

- to observe an HR (hazard ratio) equal or below to 0.39
- a true incidence rate for the SSTI equal to 0.07 (starting to count the events two weeks after the second dose)
- time to event follows an exponential distribution.

The second hypothesis of the secondary vaccine efficacy objective will be tested for all the events occurring after the first vaccination, with one-sided alpha equal to 5.89% and power 89% (both adjusted error values will be retrieved from the second group sequential test performed on the first hypothesis).

The following assumptions are made to test the hypothesis on the HR after the first dose of vaccine/placebo:

- to observe an HR below 0.43
- a true incidence rate equal to 0.12 (starting to count the events two weeks after the first dose)
- time to event follows an exponential distribution

The upper limit assumed for the HR equal to 0.43 allows to test the second hypothesis with alpha equal to 5,89% and power equal to 89%, assuming the incidence rate equal to 0.12, with the planned sample size for the first hypothesis (about 600 subjects).

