### • Sampling schedule:

Blood samples for laboratory safety evaluation will be drawn from the first 40 subjects enrolled (i.e. subjects belonging to PoP Step 1)

- Drainage samples will be taken from those subjects performing culture test as study procedures at screening (i.e. Visit 0) and from all subjects with recurrences at the time of recurrence.
- **Data collection:** standardised eCRF. Solicited AEs will be collected using a subject eDiary.
- Safety monitoring:

The enrolment and vaccination in the PoP phase will also follow a staggered approach. After safety assessment (for details refer to Section 8.6.1) of the first vaccination of the first approximately 40 subjects (randomised with a 3:1 ratio either to the GSK *S. aureus* candidate vaccine or to the placebo group) the full enrolment of the remaining subjects in the PoP phase will continue. The remaining subjects will be randomised with a 1:1 ratio either to the GSK *S. aureus* candidate vaccine or to the placebo group).

Safety of the subjects in the PoP vaccination epoch will be monitored for the entire duration of the study with an overall duration of participation for each subject of approximately 14 months (i.e. 12 months after last vaccination).

For both, PoP staggered enrolment/vaccination and the PoP full enrolment/vaccination, the investigator is not permitted to start the administration of Dose 1 for the next group and Dose 2 until receipt of the favorable outcome of the safety evaluation as described in Section 8.6.1.

During the whole study period, if the investigator becomes aware of a holding rule being met, he/she will suspend vaccination and will inform GSK immediately (e.g. in case of death or any life-threatening SAEs).

Refer to Section 8.6 for detailed description of holding rules and safety monitoring. Refer to the iSRC Charter for details about the safety assessment committees evaluation.

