### PoP:

The target enrolment of subjects is event driven (

approach:

- The first approximately 40 subjects will be randomised with a 3:1 ratio (30 subjects receiving GSK *S. aureus* candidate vaccine and 10 receiving placebo).
- The remaining subjects in the PoP epochs will be enrolled approximately 8 days after the last of the approximately 40 subjects was vaccinated (for safety evaluation and consequence on study progress refer to Section 8.6.1). The subjects will be randomised with a 1:1 ratio either to receive the GSK *S. aureus* candidate vaccine or placebo until **CO** (event driven design). It is estimated that a total of approximately 500 to 600 subjects will be vaccinated in the PoP but enrolment may continue until 27 events is reached (see Section 10.1.2).

Allocation of the subject to a treatment number at the investigator site will be performed using a randomisation system on internet (SBIR). The randomisation algorithm will use a minimisation procedure (PoP only) accounting for site and for previous SSTIs yes or no within the last 12 months. Minimisation factors will have equal weight in the minimisation algorithm.

After obtaining the signed and dated ICF from the subject and having checked the eligibility of the subject, the site staff in charge of the vaccine administration will access SBIR. Upon providing the subject identification number, the randomisation system will determine the study group and will provide the treatment number to be used for the first dose.

The number of each administered treatment must be recorded in the eCRF on the Vaccine Administration screen.

When SBIR is not available, please refer to the SBIR user guide or the Study Procedures Manual (SPM) for specific instructions.

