## 10.1.2. Sample size calculation

The incidence rates of *S. aureus* SSTI (index cases and recurrences) at the selected study centre(s) are difficult to predict. For this reason, the study is designed as an event driven trial and includes **CO**. After the dose-escalation safety lead-in epoch and the PoP staggered enrolment step of PoP vaccination epoch are concluded and no safety issues are found, enrolment will continue with a randomisation of 1:1 ratio either to the *S. aureus* candidate vaccine or to the placebo group. It is estimated that approximately 500 to 600 subjects will be needed to achieve the **CO** 

The key objective of clinical efficacy will be measured counting culture confirmed cases of recurrent *S. aureus* SSTIs occurring from 14 days after the second dose up to 12 months after the second dose. Before the second dose has elicited a proper response (i.e. from Day 61 to Day 75) subjects will be also monitored for SSTI.

The event driven design includes **CCL** (culture confirmed *S. aureus* SSTI recurrences) overall after the second dose to test the null hypothesis of no efficacy assuming an HR equal to 0.39 from Day 75 (14 days after the second vaccination) up to 12 months after the second vaccination.

The study sample size is not fixed and the enrolment will proceed until reaching the planned number of events necessary to evaluate the first statistical hypothesis of no efficacy (HR $\geq$ 1) with an overall power equal to 80% and an overall one-sided alpha equal to 7.5%.

A group sequential design with the O'Brien Fleming spending function is applied to the first hypothesis after the second vaccination, CCL

After the final analysis for the first hypothesis a sequential procedure will be used in order to control the overall type I error for the efficacy objective: starting from the first hypothesis on the efficacy after the second dose, the second hypothesis on the efficacy after the first dose will be tested only if the efficacy after two doses will be demonstrated.

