5.3. Efficacy/Effectiveness

5.3.1. Analysis of efficacy planned in the protocol

The efficacy analysis will be based on the mFAS. A supplementary analysis will be based on the PPS.

Rules for SSTI cases:

- All cases of SSTI will be reported, including multiple cases in the same subject.
- The start date of a case is the date of the visit during which the diagnosis is done by a treating physician or equivalent licensed medical professional or based on medical records review by a study physician.

• A new SSTI episode may be assessed by a study physician at site for any SSTI visit occurring after the clinical resolution of the previous SSTI and, if it does not represent a persistence of the previous episode as per medical judgement, it can be considered a new episode.

Endpoint	Statistical Analysis Methods
Key secondary	The analysis of efficacy will be based on the occurrence of the first case of SSTI anytime from 14 Days after the administration of the second dose of the study vaccine up to 12 months. All subjects from the mFAS will contribute to the comparison between the treatment and the placebo groups.
	Time to occurrence of key secondary endpoint during the defined efficacy follow-up period will be compared between groups by calculating the respective Hazard ratio
	Vaccine (VE) will be defined as 1 minus the hazard ratio times 100:
	$VE = (1 - hazard ratio) \times 100$
	Censoring will occur at the time of the last scheduled or medically attended visit without the occurrence of SSTI cases before the end of follow up. Subjects who will complete the follow up without events will be censored at 1 year.
	In order to check the statistical significance, 1-sided P-value for the log rank test will be calculated. 1-sided nominal type I error will be 1.61% at the interim analysis and 5.89% at the final analysis. The objective will be met if the 1-sided P-value calculated for the null hypothesis H0 = [occurrence SSTI VE = 0%] is lower than defined 1-sided alpha level.
Co- secondary	The co-secondary endpoint will be analysed only if the statistical significance is demonstrated for the key secondary endpoint.
	For this analysis, the FAS will account for the first case of SSTI anytime from 14 Days after the administration of the first dose of the study vaccine up to 14 months.

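### The readable success rule pools PoP Step 1 (3:1) with Step 2 (1:1) in an unstratified log-rank test, so a lower recurrence risk in Step 1 would push the one-sided type I error above 7.5%

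*Protocol*

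**What the plan says.** - **Allocation.** Protocol 7.2.2.1.1 says "The first approximately 40 subjects will be randomised with a 3:1 ratio", which is 30 vaccine and 10 placebo. Protocol 5.2.2 (safety monitoring) adds "The remaining subjects will be randomised with a 1:1 ratio". SAP section 3 repeats both ratios.
- **Minimisation.** In the PoP phase the algorithm works by "accounting for site and for previous SSTIs yes or no within the last 12 months".
- **Test.** Protocol 10.1.1 says "Both hypotheses will be tested using the log rank test". SAP Table 5 says "1-sided P-value for the log rank test will be calculated" and places the whole mFAS in one comparison for the key endpoint. Protocol 10.3.3.1 reads the same way. None of these places mentions strata.
- **Error rate.** Protocol 10.1.2 sets "an overall one-sided alpha equal to 7.5" per cent. SAP Table 5 gives the split: "1-sided nominal type I error will be 1.61% at the interim analysis and 5.89% at the final analysis".
- **Not readable.** SAP 7.2 refers to code in sections 5.3 and 5.3.2. The text after Table 5 is redacted.

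**The concern.** In Step 1 about 75% of subjects receive vaccine; in Step 2 it is 50%. Any factor that makes recurrence more or less likely in Step 1 is therefore unevenly spread over the arms of the pooled analysis. If Step 1 is lower risk, the vaccine arm holds a surplus of low-risk subjects and looks effective when it is not.

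The documents give reasons why the steps might differ, without showing that they do:

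- Clinically significant laboratory abnormality at vaccination is a PoP exclusion (protocol 6.2.1.2), but safety bloods are drawn only in Step 1 (Table 4, Table 25).
- Step 1 has clinic contacts on Days 8 and 68 where Step 2 has telephone calls.
- Amendment 4 widened PoP eligibility, though the documents do not say whether Step 1 enrolled before it.
- Protocol 10.1.2 itself describes incidence as hard to foresee.

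At stake is the error rate claimed for the only confirmatory comparison in the study.

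**Working it through.** **Inputs from the documents:** HR 0.39, incidence 0.07 from 14 days after dose 2, overall one-sided alpha 7.5%, power 80%, looks at 13 and 27 events, Step 1 split 30:10, total 500 to 600. **Assumed, because not given:** the ratio r of Step 1 to Step 2 recurrence risk, accrual of 15 to 40 subjects per month, no dropout.

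**1. The plan's own figures reproduce.** Take a two-look design at information fraction 0.48 with the classical O'Brien-Fleming boundary c/√t, where c = 1.4835.

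- Interim z = 1.4835/√0.48 = 2.141, one-sided p = 1.613%.
- Alpha added at the final look = 5.887%; 1.613% + 5.887% = 7.5%.
- With the beta boundary (8.83% + 11.17% = 20%) the required drift is 2.420. Events = 4 × 2.420² / (ln 0.39)² = 26.4, rounded up to 27.

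So 5.89% is an increment of spent alpha. The matching nominal level at the final look is about 6.9%. Used literally as p-value cut-offs, 1.61% and 5.89% give 6.55% overall in normal theory. Both readings are carried below.

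**2. Pooled hazard ratio with no vaccine effect.** With Step 2 risk set to 1 and n₂ Step 2 subjects per arm:

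HR = [(30r + n₂)/(30 + n₂)] ÷ [(10r + n₂)/(10 + n₂)]

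For N = 500, n₂ = 460/2 = 230. At r = 0.5: (245/260)/(235/240) = 0.942/0.979 = 0.962. At r = 2: (290/260)/(250/240) = 1.115/1.042 = 1.071.

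**3. Effect on type I error.** The shift in the final z is −ln(HR) × √(27/4); for HR 0.962 it is 0.039 × 2.598 = 0.10. Over both looks, with the O'Brien-Fleming boundary:

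| r | Pooled HR under the null, N = 500 to 600 | Overall one-sided alpha |
|---|---|---|
| 0.5 | 0.962 to 0.968 | 9.0% to 8.7% |
| 0.75 | 0.981 to 0.984 | 8.2% to 8.1% |
| 1 | 1.000 | 7.5% |
| 2 | 1.071 to 1.060 | 5.3% to 5.6% |
| 3 | 1.136 to 1.117 | 3.9% to 4.3% |

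Under the null, 27 events need only 27/0.07 = 386 subjects, so Step 1 weighs more: 9.4% at r = 0.5, 8.4% at 0.75, 4.9% at 2. With the literal 1.61%/5.89% cut-offs, normal theory gives 7.7% to 8.3% at r = 0.5, and at 0.75 the error stays at 7.1% to 7.4%, below 7.5%.

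**4. Simulation of the log-rank test itself** (enrol 30:10, then 1:1, test at 13 and 27 events; ranges cover both boundary readings and the accrual rates tried; Monte Carlo SE about 0.3 points):

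| r | Pooled | Stratified by step |
|---|---|---|
| 0.5 | 8.4% to 10.1% | 6.2% to 7.4% |
| 0.7 | 8.6% to 9.3% | 6.4% to 7.7% |
| 1 | 6.4% to 7.8% | 6.1% to 7.5% |
| 2 | 4.0% to 5.0% | 6.5% to 8.0% |

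The pooled test moves with r. The stratified test stays near its equal-risk level.

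**5. Power at HR 0.39** (futility not applied).

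- r = 2: pooled power falls from 83.0% to 78.8% with the O'Brien-Fleming boundary, and from 80.7% to 76.9% with the nominal cut-offs, about 4 points each; the widest estimate was about 6. Stratified power is 81.7% and 80.1% respectively.
- r = 1, cost of stratifying: with the nominal cut-offs, 79.4% pooled against 79.4% stratified, or 80.7% against 79.7%; with the O'Brien-Fleming boundary, 83.0% against 81.8%, or 85.7% against 81.6%.

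**6. Leaving out the minimisation factors.** An unadjusted log-rank test at a 7.5% level after minimisation on two factors gave 6.4% to 6.9%, against 7.7% to 8.2% under simple randomisation (SE about 0.4 points; 30% with previous SSTI assumed).

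**The case against.** The strongest reply is that the effect may not exist and is limited if it does. No risk difference between steps is documented. Step 1 is about 40 of 500 to 600 subjects and at incidence 0.07 contributes about 40 × 0.07 = 2.8 events under the null. In the pooled simulations the error at equal risk already runs up to 7.8%, so not all of the excess over 7.5% comes from step. Efficacy is a secondary objective in a study described as a preliminary evaluation. All of this stands, and it limits the size of the point. It does not remove it: the plan makes a numerical error-rate claim that, as written, depends on equal risk in the two steps.

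Two stronger readings are tempting and are not supported.

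- A reader might infer that any step difference breaks the 7.5% rate. It does not. A higher Step 1 risk makes the test conservative and costs power instead.
- A reader might infer that the analysis ignores the minimisation factors and is biased by that. The documents do not show it. The relevant SAP code is redacted, and the SAP reference list includes Cox regression and a permutation test for covariate-adaptive randomisation, neither cited in the readable text. In any case, leaving these factors out makes the log-rank test somewhat conservative; it does not favour the vaccine.

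**Conclusion.** The point holds for step, in one direction for the error rate and in the other for power. With Step 1 risk at half that of Step 2, overall one-sided type I error of the pooled test is about 9% to 10%, somewhat lower if 1.61% and 5.89% are applied literally as cut-offs. At 0.7 times it is about 8% to 9%. At twice the risk it is about 5%, with about 4 to 6 points of power lost. These figures rest on assumed risk ratios and accrual. The documents give neither the size nor the direction of any difference, and redacted SAP text may already deal with it. This is a cheap improvement to make, not a demonstrated failure of the design.

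**What to change.** In protocol 10.1.1 and 10.3.3.1 and in SAP Table 5, define the confirmatory log-rank test as stratified by PoP step (1 or 2) at interim and final, and estimate the hazard ratio from a Cox model with the same strata. Keep the pooled test as a sensitivity analysis. State how minimisation is handled in SAP 5.3.2; if that section already accounts for step, align the visible rule with it.

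Stratifying also by previous SSTI is optional. It could gain a little efficiency but corrects no bias, and the joint four-stratum test has not been checked at 27 events.

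The cost is wording and one strata term, with no extra events. If the steps have equal risk, power falls by 0 to 1 point with the nominal cut-offs and by up to about 4 points with the O'Brien-Fleming boundary, remaining at about 80% or more.

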7.2. Statistical considerations for interim analyses

One interim analysis for efficacy and futility will be done following a group sequential design for the key secondary efficacy analysis. The interim analysis is event driven and is planned when 48% of the assumed total number of culture confirmed cases of recurrent *S. aureus* SSTIs (13 events after the second vaccination) will be observed and it may stop the enrolment of the study for efficacy or futility.

In case of stopping for efficacy at the interim analysis, also the second secondary efficacy endpoint will be tested with the same alpha used for the first hypothesis (alpha=1.613%). Enrolment maybe stopped if the null hypothesis is rejected (efficacy) or accepted (futility) after the interim analysis, but the follow up of subjects will continue for 12 months after the second dose.

The design assumes that 2 sequential tests are made for the key efficacy objective using test boundaries (binding for efficacy and not binding for futility) calculated by the O'Brien-Fleming spending function and assuming that time to event follows an exponential distribution. An adjusted alpha equal to 1.613 % and a beta equal to 8.83% (or a power equal to 91%) will be spent at the interim to reject or accept the null hypothesis for the key efficacy objective with a sample of 13 cases. At the final analysis the adjusted alpha and beta will be, respectively, 5.89% and 11.17% (or a power equal to 89%) with a sample of 27 cases. The final alpha and beta after the two sequential tests will be kept to 7.5% and 20%. The secondary efficacy endpoint will be tested at the final analysis after rejecting the null hypothesis for the key objective.

The proc SEQDESIGN is used for the planning of the test boundaries with the code reported in the section 5.3. The output with the limits is used in the proc SEQTEST (see section 5.3.2)

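### Protocol 10.1.1 and SAP 7.2 print one minus each incremental beta as a power (91% at the interim, 89% at the final) for a test whose overall power is 80%

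*Protocol*

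**What the plan says.** Protocol 10.1.1 describes two looks at the first hypothesis (hazard ratio after the second dose, log-rank test), at 48% and 100% of the planned events. For the interim it states: "At the interim analysis the first hypothesis will be tested spending 1.61% alpha and 8.83% beta (this means a power equal to about 91"%). For the final: "At the final analysis the alpha will be 5.89% and the beta 11.17% (this means a power equal to about 89"%). The next sentence gives the totals as a cumulative alpha of 7.5% and "the cumulative beta 20% (or power equal to 80"%). Protocol 10.1.2 repeats that the trial is sized "with an overall power equal to 80% and an overall one-sided alpha equal to 7.5"%.

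SAP 7.2 carries the same labels, with 13 events at the interim: "a beta equal to 8.83% (or a power equal to 91%) will be spent at the interim". For the final look it gives "11.17% (or a power equal to 89%) with a sample of 27 cases". It then closes with the totals: "The final alpha and beta after the two sequential tests will be kept to 7.5% and 20"%. The same section says of the interim that "it may stop the enrolment of the study for efficacy or futility".

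**The concern.** Three powers are printed for one hypothesis: 91%, 89% and 80%. Rejecting at the interim, or at the final, is one way of rejecting overall, so the probability at either look cannot exceed the overall power. Cumulative power also cannot fall from 91% at 13 events to 80% at 27.

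The interim can stop enrolment for efficacy. A reader of the legible text would put the chance of that at 91% if the vaccine works as assumed. Such a reader could take a result in the continue region as evidence against the vaccine, although under the design assumptions it is the most likely result.

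**Working it through.** **Inputs.** Hazard ratio 0.39, log-rank test and the alpha and beta portions (Protocol 10.1.1). One-sided testing, 7.5% alpha and 80% power overall (Protocol 10.1.2). Events 13 and 27, interim alpha 1.613%, futility non-binding (SAP 7.2). Allocation is taken as 1:1, ignoring the 3:1 ratio in the first 40 or so subjects.

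**1. The plan's own design reproduces.**
- 1.61% + 5.89% = 7.5% and 8.83% + 11.17% = 20%, so the stage figures are increments.
- Classic O'Brien-Fleming boundaries at 48% information give alpha increments of 1.613% and 5.887%, as stated.
- With the stated increments and non-binding futility, 80% power needs 26.4 events, rounded up to 27.

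**2. Where 91% and 89% come from.**
- 1 − 0.0883 = 0.9117 and 1 − 0.1117 = 0.8883.
- On the plan's increments, a trial with hazard ratio 0.39 that follows the futility rule succeeds at one of the two looks (80%), stops for futility (8.83%), or continues and then fails (11.17%).
- So 91.17% = 80% + 11.17%. This is the chance of not stopping for futility, and it counts trials that continue and fail.
- Likewise 88.83% = 80% + 8.83%, which counts trials stopped for futility. Neither figure is a probability of rejecting the null.

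**3. Interim at 13 events (log-rank normal approximation).**
- Drift = −ln(0.39) × √(13/4) = 1.698.
- Efficacy boundary for one-sided 1.613%: z = 2.141. Crossed with probability Φ(1.698 − 2.141) = 0.329.
- Futility boundary for 8.83% beta: z = 1.698 − 1.351 = 0.346 (from unrounded values). Crossed with probability 0.088.
- Continue: 1 − 0.329 − 0.088 = 0.583.

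Other methods for the efficacy probability:

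| Method | Result |
|---|---|
| Freedman: drift (0.61/1.39) × √13 = 1.582; Φ(1.582 − 2.141) | 0.288 |
| Exact split: at most 2 of 13 cases on vaccine, p = 0.39/1.39 | 0.248 |
| Simulated log-rank, 40,000 runs, 275 or 300 per arm, no censoring before the 13th event | about 0.24 |

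The exact test stops at 2 vaccine cases (null probability 0.011), because 3 has null probability 0.046 and exceeds 1.613%.

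**4. What 91% would require.** Events = 4 × (2.141 + 1.351)² / ln(0.39)² = 55.0, about twice the planned total. With 13 events, the hazard ratio would have to be near exp(−2 × 3.492/√13) = 0.14.

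**5. Final at 27 events.**
- Drift = 0.9416 × √(27/4) = 2.446.
- A single look with no interim has power 0.811 at one-sided 5.89% and 0.843 at the full 7.5%. Neither reaches 89%.
- Two looks with correlation √(13/27) and futility followed give cumulative power 0.789 if the final nominal level is 5.89%, and 0.806 if it is about 6.9% (the level that spends the full 7.5%). Both are about 80%.
- Success given continuation: 0.461/0.583 = 0.790 or 0.477/0.583 = 0.818.

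**The case against.** The strongest reply is that this is loose wording in a sound design. Protocol 10.1.1 says the errors are being spent, and it adds them to 20% beta and 80% power in the same paragraph. SAP 7.3 decides by comparing the test statistic with the boundaries. The interim is run by an independent data analysis centre, and SAP 7.1 lists it as internal. All of that stands, and it limits the consequence to misreading. It does not make 91% or 89% a power, and the same word is used alongside for the true 80%.

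A second reply is that 33% is the highest of four estimates. With 13 events the discrete test gives nearer 24% or 25%. That also stands, so the range should be printed. The 33% comes from the approximation that reproduces the plan's 80%, and the lower figures only widen the gap from 91%.

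Third, the second-hypothesis text in Protocol 10.1.1 takes its error values from the final test of the first hypothesis and also states 89%. The error values it draws on, 5.89% and 11.17%, remain printed after the edit. The power of the second hypothesis is a separate calculation and is not challenged here, but its sentence should be read alongside the change.

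Finally, parts of SAP 5.3 are blacked out and may hold stage-wise probabilities. Those would not correct the legible statements.

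**Conclusion.** The point holds. Neither printed stage power exists in the design for the first hypothesis. Under a hazard ratio of 0.39 and 1:1 allocation, the chance of declaring efficacy at 13 events is about 33% by the log-rank normal approximation and 24% to 29% by the other methods, against the printed 91%. At 27 events no reading of power reaches 89%: the ceiling is 84% for a single look at the full 7.5%, and success given continuation is 79% to 82%. The stated overall power of 80% is right, at 78.9% to 80.6% with futility followed. If the non-binding futility boundary is ignored, it is 81.7% to 83.7%. Which nominal level applies at the final look is a separate question and does not affect this conclusion. The text should be corrected, but no boundary, event number or decision rule is affected.

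**What to change.** In Protocol 10.1.1 and SAP 7.2, delete the parenthetical powers of 91% and 89% (four deletions in all). Label 8.83% and 11.17% as incremental beta, with cumulative beta 20% and overall power 80%. Add one sentence to each document, for example:

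> At a hazard ratio of 0.39, by the log-rank normal approximation, the interim at 13 events crosses the efficacy boundary with probability about 33% (24% to 29% by Freedman, exact and simulated calculations), crosses the futility boundary with about 9%, and continues with about 58%; cumulative power at 27 events is about 80% if the futility boundary is followed.

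The cost is wording only. Boundaries, event numbers, alpha, overall power and the second-hypothesis text stay as they are.
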